Secondary Objectives: To test hypothesis that 12-weeks of BID tvCVS treatments increase functional connectivity in the brain.

Exploratory Objectives: This study will seek to establish the relationships between changes in cerebral perfusion and CVR with improvements in clinical endpoints and to evaluate whether these changes are durable (at an assessment five weeks after the cessation of treatments). Furthermore, the feasibility of detecting change in cerebrovascular reactivity (CVR) as assessed via transcranial Doppler sonography (TCD) will also be explored as well as pulse wave velocity (PWV).

Study Design

A double-blinded, randomized trial comparing two different neurostimulation patterns will explore the effects of tvCVS treatments on changes in biomarkers of neurovascular status (i.e. cerebral blood flow perfusion and cerebrovascular reactivity) as well as their relationship to clinical endpoints. Eligible and enrolled participants will be randomly allocated in a 1:1 ratio using block randomization by the clinical site. Participants will be trained in the clinic to self-administer device treatment and then will continue to self-administer the ~19-minute treatments twice daily for 12 weeks in the home. Individual stimulation sessions will be spaced a minimum of 1 hour apart. Outcome measures will be administered at the baseline, the end of the 12-week treatment period and at 5 weeks post-treatment. Study participants will continue to take their approved PD medications throughout the study and will maintain patterns of usage throughout.

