Participants will be screened for COVID-19 upon arrival to the clinic. A bilateral ear exam will then be performed. A pregnancy test will be performed for all female participants of childbearing age. The MDS-UPDRS part III and the Timed Up and Go (TUG) will then be administered. Participants will then undergo the Magnetic Resonance Imaging (MRI) protocol (see below) and the transcranial Doppler sonography recordings of a hypercapnia challenge. Pulse wave velocity may be measured at this time.

After the collection of baseline neuroimaging data, participants will return to the clinic where they and their caregivers will try on an unpowered Device, will be randomized and trained on the use and care of the tvCVS Device. The Device will be allocated to the participant and the coordinator should note the Device ID in the Device Inventory Control Log. The study coordinator will assist the participant in adjustment of the headset settings. See Clinical Coordinator Quick Reference Guide for procedures. Once the participant confirms that the headset is comfortable enough to proceed, the participant will be randomized by selecting an envelope with printed bar code from the pack of four. Note that a given pack of 4 should be completed before a new pack is opened. The study coordinator will load the prescription on the Device and then place the unopened envelope in the study binder. * Envelopes should be only be opened under circumstances where treatment allocation must be known for management of an adverse event. Once the Participant has demonstrated proficiency in Device care and use procedures, they will take their designated Device home and will self-administer treatments twice daily during the treatment period. Participants will also be provided with a detailed handout (step-by-step guide with pictures), for self-administration of device treatments. Coordinators will also call the participant the next day to confirm that the participant was able to

administer treatments. If necessary, additional training sessions via telemedicine may be scheduled.

MRI protocol:

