The Generation 4.0 TNM™ device uses a bar code reader to import a coded waveform. The use of the bar code aids blinding during randomization since the QR code is not readable by staff members. Bar codes will be printed on sealed envelopes that contain the treatment allocation information inside. A note will be printed across the seal of all envelopes and the study staff will be instructed that envelopes should only be opened at the site in the case of a SADE or UADE that requires the designated Unblinding Investigator to become unblinded to treatment allocation.

For randomization, the training coordinator will simply scan the bar code on the envelope and then leave the unopened envelope in the study participant's binder. Should treatment allocation information be required for handling of an AE, a CRF providing the details of the incident will be documented. The Device Sponsor's CRA will check to ensure envelopes have remained sealed at monitoring visits and at study close out.

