Packets containing 4 sealed envelopes with the printed bar codes for randomization assignments will be provided by the Device sponsor. Each batch will contain two stimulation 1 and two stimulation 2 assignments. The envelopes will be randomly shuffled by an agent not involved with the study. A given packet will be completed before the next packet is opened. The device-training coordinator will load the treatment onto the device, will record the device number allocated to the participant and will train the participant according to the training script provided (see Study Coordinator Quick Reference Guide). If the participant makes a comment about feeling warming or cooling sensations that may potentially unblind the study staff to treatment allocation, this information is not to be shared with other study staff including other coordinators, the principal investigator, Device sponsor CRA, data analysts or the study statistician. All assessments will be performed by a study coordinator that does not take part in the interim phone calls. Participants will be told that pain should not be associated with treatment, and if they do experience pain, that they should stop treatment and contact the coordinator immediately and/or seek medical attention if necessary. However, they will also be told that in the absence of pain, for the integrity of the trial, they should not discuss their treatment experience with anyone associated with the study (e.g. other research staff, their caregiver or other people they may know are participating in the trial). The exception being when they are specifically asked about their treatment experience in the Device Usability Questionnaire at the end of the treatment period.

Unblinding at the study site will only occur in the case of a SADE (serious adverse event at least possibly related to the device) or UADE (serious and unanticipated/unexpected adverse events at least possibly related to the device) that also requires cessation of device treatment. If this situation seems likely, the Unblinding Investigator, noted in the Delegation of Authority Log, should contact SNS to request approval to unblind. Upon receipt of written permission from the

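### Disclosed 2:2 packs of four, finished one at a time, let the randomising coordinator deduce some allocations: at most a third in advance, and only if all earlier ones in the pack are known

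*Combined protocol and SAP*

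**What the plan says.** *Study Design* has participants "randomly allocated in a 1:1 ratio using block randomization by the clinical site". *Randomization, Blinding and Unblinding* gives the mechanism: "Packets containing 4 sealed envelopes with the printed bar codes for randomization assignments will be provided by the Device sponsor", and "Each batch will contain two stimulation 1 and two stimulation 2 assignments". An agent outside the study shuffles the envelopes.

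Under *Baseline imaging / Device training visit*, "the participant will be randomized by selecting an envelope with printed bar code from the pack of four", with the instruction "Note that a given pack of 4 should be completed before a new pack is opened". This step comes after the baseline ratings and imaging.

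The person handling the envelope is named: "the training coordinator will simply scan the bar code on the envelope". The same coordinator loads the device and trains the participant. Staff cannot read the code, the envelope stays sealed, and the sponsor's monitor checks the seals.

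On leakage, the plan has a rule that begins "If the participant makes a comment about feeling warming or cooling sensations that may potentially unblind the study staff to treatment allocation". Its consequence is that the hearer must not tell other staff. It does not remove the hearer from later randomisations or from rating.

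The one rule separating raters from other staff is "All assessments will be performed by a study coordinator that does not take part in the interim phone calls".

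**The concern.** Sealed envelopes and unreadable codes stop staff from reading an allocation. They do not stop staff from working one out when the total in each pack is known. Once both envelopes of one arm are known to be used, whatever remains in the pack belongs to the other arm. A coordinator who has picked up allocations from some participants can therefore learn those of others who said nothing.

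The stake is mainly the clinical ratings made by a coordinator, notably MDS-UPDRS part III and the Timed Up and Go. *Analysis Plan* correlates changes in these measures with changes in the imaging measures. If the trainer also rates, deduced allocations can colour the week-12 and week-17 scores. An allocation foreseen before randomisation could likewise colour the baseline part III and Timed Up and Go, which are done earlier at the same visit.

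**Working it through.** The plan gives no predictability figure to reproduce. Its counts are consistent: 20/4 = 5 packs, and 5 × 2 = 10 per arm.

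**Inputs**
- Pack of 4, split 2:2, with known boundaries (*Randomization, Blinding and Unblinding*; *Baseline imaging / Device training visit*).
- Up to 20 participants at one site, at most 4 enrolled per month (*Sample size*).
- p, the probability that any one earlier allocation in the pack is correctly inferred. This is an assumption, since the documents give no value. Inferences are taken as independent, and the range 0.25 to 1 is shown.

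**Ceiling, all earlier allocations known (p = 1).** The six equally likely orders are AABB, ABAB, ABBA, BAAB, BABA and BBAA. Positions 1 and 2 are never certain. Position 3 is certain only in AABB and BBAA, so with probability 2/6 = 1/3. Position 4 is always certain. The expected share is (0 + 0 + 1/3 + 1)/4 = 1/3, and 20 × 1/3 = 6.7 participants. Over five packs the count is 5 + Binomial(5, 1/3), so between 5 and 10.

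**Partial knowledge.** Certainty requires that both used envelopes of one arm have been identified, which has probability p². Position 3 is then certain with probability p²/3 and position 4 with probability p². The share is (p²/3 + p²)/4 = p²/3.

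| p | Certain in advance | Of 20 | Best-guess success (chance 50%) |
|---|---|---|---|
| 1 | 33.3% | 6.7 | 70.8% |
| 0.8 | 21.3% | 4.3 | 65.7% |
| 0.5 | 8.3% | 1.7 | 59.9% |
| 0.25 | 2.1% | 0.4 | 55.4% |

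**Deduction after the pack is used up.** For rating bias, the allocation need not be known before randomisation. A silent participant is identified once both pack-mates in the other arm are known, which has probability p²: 64% at p = 0.8, 25% at 0.5 and 6.25% at 0.25. At the enrolment cap of 4 per month a pack fills in about a month, before its members reach week 12.

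**Other block sizes.** With all earlier allocations and the block boundaries known, the certain share for a block of 2m is 1/(m + 1): 25.0% for blocks of 6, 20.0% for blocks of 8, and 1/11 = 9.1% (1.8 of 20) for a single block of 20. Blocks of varying size that the site does not know also take away the boundaries. No figure is put on that gain, because it depends on the sizes chosen.

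**The case against.** The strongest reply is that p is unlikely to be near 1. Several provisions work against it:
- Stimulation 2 also starts with a cooling sensation, and the earpieces then warm to body temperature (*Description of Study Intervention*). A bare remark about cool or warm therefore does not identify the arm.
- Participants are not told that the device works through temperature, and are asked not to discuss their treatment experience.
- Treatment takes place at home. After training, the first scheduled contacts are the next-day call and week 3, so at full enrolment pace a pack could be used up with little to learn from.
- In the earlier trial, participants' guesses indicated that blinding held. That evidence is indirect, because it concerns participants and not coordinators.

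These points stand and are why one third is only a ceiling. They do not bring p to zero. Stimulation 1 heats one ear, cools the other and swaps sides every two days, and a participant who describes that pattern is informative. The plan itself foresees such comments.

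A reader might infer three stronger things that the documents do not support:
- *The trainer will rate outcomes.* The text is silent; it states no overlap. The next-day call is listed among the interim calls, so a trainer who makes it is already excluded from rating. However, the caller is described only as a coordinator, so this is not assured.
- *Foreknowledge will steer enrolment.* Randomisation follows consent, eligibility, baseline ratings and imaging, and it is the participant who confirms that the headset is comfortable. Little discretion remains, so this is a minor route.
- *The primary results are compromised.* Perfusion and reactivity are measured by pCASL and are not rater-scored, and endpoint analysts are blinded. The link between imaging and clinical change is an exploratory objective.

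It is also fair to say that packs shuffled by an outside agent are a valid randomisation. The weakness is predictability, not a lack of randomness.

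**Conclusion.** The point holds as a modest, cheaply removed weakness in concealment and staff blinding. Because block size, content and boundaries are all known to the coordinator who randomises and trains, the allocations of silent participants can be deduced from known pack-mates. The ceiling of 6.7 of 20 certain in advance needs every earlier allocation in the pack to be correctly known. With independent partial knowledge the share falls as p²/3, to 1.7 of 20 at p = 0.5 and 0.4 at p = 0.25. The documents do not say where in that range the trial will lie, so it should not be read as a forecast that a third of allocations will be known. The consequence for the ratings is conditional on the trainer also rating, which the assessor rule leaves open.

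**What to change.** Have the independent agent prepare one list with varying block sizes that are neither disclosed to the site nor stated in the site protocol. Supply sequentially numbered, sealed, bar-coded envelopes to be used strictly in order, replacing selection from a pack of four. Amend *Baseline imaging / Device training visit* and *Randomization, Blinding and Unblinding* accordingly.

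Where existing staffing allows, extend the assessor rule so that the assessor also takes no part in device training. This also covers comments that the trainer hears directly, which no change of block size can address. The documents give no staffing numbers, so whether it needs another person cannot be judged from them.

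The cost is re-printing the envelopes and amending several sentences in those two sections. Arm sizes may differ slightly if enrolment stops inside a block; the present packs already allow a difference of up to two. If the total is fixed at 10:10, the last envelope remains predictable to anyone who knows all the others.

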After the completion of the MRI scan, the coordinator will accompany the study participant to the clinic for TCD recordings. There, the participant will receive a second hypercapnia challenge (using the same conditions described above) while undergoing TCD recording. Pulse wave velocity (PWV) may be measured at this time.

Treatment period:

All participants will treat twice daily, at least one hour apart. Each treatment duration is 19 minutes 39 seconds. Participants will only wear the device when administering a treatment per protocol. The treatment period is anticipated to last for 12 weeks. However, treatment may be

extended for approximately 2 additional weeks in the case of scheduling conflicts (such as those imposed by standard operating procedures imposed by WFU to limit the spread of COVID-19). Patients should continue to treat twice daily up until the time of the end of treatment clinic visit.

Interim phone calls:

- Participants will be called the next day after their Device training visit to confirm that participants were able to successfully administer treatment in the home setting.
- Scheduled follow up phone calls will be made at week 3, week 6 and week 9. During these calls, the coordinator will ask about any adverse events, any changes to concomitant medications and to confirm no issues have arisen with use of the Device.
- Participants will also have received the contact information for the site coordinator so that they may report potential adverse events or issues with the Device in real time.

End of treatment visit (remote) – week 12:

During this remote visit, the study coordinator will administer the NMSS, the MDS-UPDRS parts II and IV as well as the modified MDS-UPDRS part III. They will also administer the MoCA, the MRI safety screening as well as a Device usability questionnaire. Participants will then be asked to completed the (PROs) including the Geriatric Depression Scale (GDS), the Parkinson's Anxiety Scale (PAS), the Epworth Sleepiness Scale (ESS), the Functional Assessment of Chronic Illness Therapy – Fatigue (FACIT-F) and the Device Usability Questionnaire and to bring them to their scheduled imaging visit. Participants will also be told to bring their Devices with them to the next clinic but that they should continue with twice daily treatments until their imaging visit.

End of treatment visit (in clinic)- week 12, 1 day after remote visit:

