Therapeutic CVS has been studied for use in prevention of episodic migraine and in treatment of symptoms of Parkinson's Disease. Results of these studies (including one multisite RCT and one single-site RCT, respectively), resulted in neither serious nor unanticipated/unexpected adverse events related to the study device. Additionally, there was no reduction in balance and no negative change in either mood or cognition.

The following AEs are known, possible side effects of using the investigational device:

More likely:

- Drowsiness
- Dizziness (whirling or spinning sensation; may also be called “giddiness” or vertigo)
- Treatment site discomfort (skin itching, skin irritation felt within the ear canal or around the ear canal or pressure felt within ear canal)

Less likely:

- Nausea
- Vomiting
- Tinnitus
- Headache

All of the potential AEs noted above are expected to resolve soon after use of the investigational device is stopped.

Serious Adverse Device Effect (SADE):

Adverse device effect that has resulted in any of the consequences characteristic of a serious adverse event.

Unanticipated Adverse Device Effect (UADE):

An Unanticipated Adverse Device Effect is a *serious* adverse effect on health or safety or any life-threatening problem or death caused by, or associated with, a device, if that effect, problem, or death was not previously identified in nature, severity, or degree of incidence in the investigational plan or application (including a supplementary plan or application), or any other unanticipated serious problem associated with a device that relates to the rights, safety, or welfare of subjects.

Procedures for AEs

- **Documentation and assessment**

- Following the informed consent process, clinical study participants will be routinely monitored for AEs at study visits and during telephone contacts from the clinical research staff. All AEs, regardless of treatment group, severity or suspected causal relationship to the investigational device, will be recorded on the participants’ source documentation.
- For all AEs, sufficient information will be obtained as to 1) determine the severity of the event (i.e., whether the event should be classified as “*serious*”); 2) assess the causal relationship between the adverse event and the investigational device; and 3) determine the outcome of the event.
- AEs will be followed until the event (or its sequelae) resolves or stabilizes at a level acceptable to the investigator and Device sponsor.

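### The rater rule excludes only the coordinator who makes interim calls, so the device-training coordinator, who may hear unblinding remarks, can still rate the clinical outcomes at weeks 12 and 17

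*Combined protocol and SAP*

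**What the plan says.** The relevant text is in the combined protocol and SAP, under Randomization, Blinding and Unblinding. One paragraph does three things in sequence.

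- It gives training to a named role: "The device-training coordinator will load the treatment onto the device, will record the device number allocated to the participant and will train the participant".
- It then recognises a leak, a "comment about feeling warming or cooling sensations that may potentially unblind the study staff to treatment allocation", and sets one remedy: "this information is not to be shared with other study staff including other coordinators". The non-disclosure list also covers the principal investigator, the sponsor's monitor, the data analysts and the statistician.
- It then restricts who may rate: "All assessments will be performed by a study coordinator that does not take part in the interim phone calls".

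The calls themselves are described under Interim phone calls: "Participants will be called the next day after their Device training visit to confirm", and "Scheduled follow up phone calls will be made at week 3, week 6 and week 9". The section on the baseline imaging and device training visit adds that further training by telemedicine may be arranged if needed. On safety, Procedures for AEs says that "clinical study participants will be routinely monitored for AEs at study visits and during telephone contacts from the clinical research staff".

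**The concern.** The non-disclosure rule protects everyone except the person who heard the remark. The rater rule should cover that person, but it is drawn around a different contact, the interim calls. The plan has already accepted that staff who talk to participants about their treatment should not rate them, and the trainer has comparable exposure.

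At stake are the scales that a coordinator administers or scores after randomisation: MDS-UPDRS, NMSS, MoCA and Timed Up and Go. Their change scores enter the correlations described in the Analysis Plan, which are meant to show whether the physiological changes underlie the symptomatic benefit. A rater who believes that they know the arm could shift the clinical difference between arms, and through it the apparent link to imaging. With enrolment capped at 20 (Sample size), a few participants rated this way could matter.

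**Working it through.** No formula applies: the point concerns who may do what, and the plan states no figure to reproduce. The check is to set side by side every place that assigns training, calls, rating or blinding.

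1. **Rater exclusions.** There is one, for the interim calls. No section excludes the device-training coordinator.
2. **Indirect exclusion through the calls.** The next-day call is listed among the interim calls, so a trainer who made it would be barred. The baseline visit section says only that coordinators make this call, and the Interim phone calls section gives the later calls to an unspecified coordinator. No section assigns any call to the trainer.
3. **Additional training.** The optional telemedicine sessions would come after home treatment has begun, when a participant has more to report. They are not listed under Interim phone calls, so running one does not trigger the exclusion.
4. **Job titles.** The baseline visit section has the study coordinator load the prescription. The remote visit sections for weeks 12 and 17 have the study coordinator do the ratings. The same title serves both, and the in-clinic MDS-UPDRS part III and Timed Up and Go name no rater. Titles therefore do not separate the roles.
5. **Other blinding statements.** The statement that endpoints are analysed blind concerns analysis, not rating. The blinded assessor mentioned under Background, Rationale and Context belongs to the previous trial.
6. **Timing.** Baseline ratings come before randomisation, so allocation cannot affect them. The exposure is at weeks 12 and 17.
7. **How informative a remark is.** Under Description of Study Intervention, active treatment takes one ear from body temperature to 42 °C and the other from body temperature to 17 °C, with the ears switched every 2 days. Control earpieces start at room temperature, feel cool, and then warm to body temperature. A remark about coolness or warmth fits either arm. A description of one hot and one cold ear, or of repeated cycling, would be far more telling.
8. **Two related contacts.** The Schedule of Activities places adverse-event review at the week-12 and week-17 visits, and nothing sets its order relative to the ratings. The week-12 remote visit also has the rating coordinator administer the Device usability questionnaire, although the same section lists it among the forms that participants complete. It is the one place where participants may describe their treatment experience. The week-12 in-clinic ratings come the next day and the week-17 ratings follow later.

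**The case against.** The permission is by omission. No section says that the trainer will rate. Training has its own role name, and withholding remarks from other coordinators suggests that a separation was intended. The delegation log and the Quick Reference Guide, which are not in the documents, may already enforce it, and a trainer who makes the next-day call is already barred. Leaks are also made less likely: participants are asked not to discuss their treatment experience with study staff and are not told that the device works by temperature, the headset is tried on unpowered, and no section requires a powered session at training. Part III may be videotaped, which would allow re-rating.

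All of this stands, and it lowers the probability of harm. It does not close the gap, because the protocol's own rule, followed exactly, still allows the trainer to rate.

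A reader might infer more, but the documents do not support these stronger readings:

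- **That one remark reveals the arm.** Control earpieces also cool and then warm, and the plan says only that a remark may unblind.
- **That reported ear discomfort points to the powered arm.** The listed side effect includes pressure in the ear canal, headset pressure is the same in both arms, and no adverse-event rates by arm are given.
- **That the bias can be put in scale points.** The documents give neither the frequency of remarks, nor how often the trainer would rate, nor the shift that knowledge would cause.
- **That the trial's main result is at risk.** The primary and secondary objectives rest on imaging, endpoint analysts are blinded, and the imaging-clinical relationship is exploratory. GDS, PAS, ESS, FACIT-F and MDS-UPDRS part IB are patient-reported.

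**Conclusion.** The point holds as a low-cost improvement to a rule that falls short of its own purpose. The plan recognises that the person who hears a temperature remark may be unblinded, yet it leaves the most obvious such person, the trainer, free to rate. The effect is confined to staff-rated clinical outcomes at weeks 12 and 17 and to the exploratory correlations built on them; the pCASL primary measures are not affected by this route. The documents do not allow the size to be estimated.

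The conclusion rests on two assumptions: that the site documents not available here do not already separate the roles, and that the warning about remarks, which refers to study staff generally, applies to the trainer. The second is a fair reading, since the warning directly follows the training sentence and refers to other coordinators.

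**What to change.** Replace the rater sentence under Randomization, Blinding and Unblinding with wording such as:

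*Post-baseline clinical ratings will be performed by a study coordinator who takes part in neither device training (initial or additional) nor the interim phone calls for that participant.*

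Assign training and calls to one coordinator and record this in the delegation log. The plan already needs a rater separate from the caller, and the caller can also train, so this change adds no role.

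Two smaller changes belong in the visit instructions:

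- At weeks 12 and 17, complete the clinician ratings before adverse-event review at the same visit. This needs no second coordinator. It reduces the leak without removing it, because the in-clinic ratings come the day after the remote visit.
- Where staffing allows, have the training/call coordinator administer the week-12 Device usability questionnaire, since later ratings follow it.

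The cost is a protocol wording change, a delegation-log entry and less flexible visit staffing.
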